Diet will be assessed via parent report food screener[21]. Items will be scored by four possible response categories and responses consist of the following: 0 ('child did not consume'), 1 ('child consumed a little'), 2 ('child consumed some'), and 3 ('child consumed a lot') with those individual items. Individual food items will be grouped in accordance with the Healthy Meal Index (HMI) [22]. Food categories include; fruits, vegetables, dairy (non-sugar based), convenience foods, sweets and desserts and sugar sweetened beverages. Consumption will be dichotomized (i.e., 'did' vs. 'did not' consume) and reported as mean days/week [21]. Two variables will be created for analysis of diet; healthy foods/drinks (fruits, vegetables, and dairy), unhealthy foods/drinks (convenience foods, and sweets/desserts, sugar sweetened beverages).

Sample Size

The above selection criteria will yield 60 children in each arm of the study. Previous studies have shown that samples of 60-100 participants provide reliable estimates of statistical and recruitment parameters upon which subsequent large-scale trials can be based [23].

Randomization

A total of 180 children will be randomly selected to participate in the study. Of the 180 children, 60 will be enrolled in 21C program. Children will not randomly assigned to the 21C program as the participating school declined random assignment of these children. The remaining 120 (i.e., n=60 in 2018 and n=60 in 2019) will randomly allocated to one of two conditions HSL or control (no program) using a random number generator. Random assignment will be completed by the study principal investigator who will not be involved in data collection and will be completed each summer after participants enrolled in the study using the runiform command in Stata (v14.2, College Station, TX). Once implemented randomization cannot be changed.

Data Analysis

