All analyses will be completed using Stata (v14.2, College Station, TX) with α levels set to $P < 0.05$. Data will be assessed for normality and descriptive statistics of programs, child characteristics, and outcome variables at baseline. The analyses will be estimated using an intent-to-treat approach [24, 25]. Multilevel mixed effects linear regressions with measures nested within children will be estimated. Separate models will be estimated for each dependent variable and included dummed group (control, HSL, 21C), time (baseline, post-summer, post schoolyear), and all group-x-time interactions. All analyses will include baseline scores on the dependent variable, age, gender, race, and year of participation as covariates in the models. Missing data will be handled using full information maximum likelihood estimates [26, 27]. The Benjamini-Hochberg procedure with a false discovery rate of 10% will be utilized to account for multiple comparisons [28].

1. *The Effect of Nutrition Education on Third Graders' School Lunch Consumption in a School Offering Food Pyramid Choice Menus.* 1998. p. 34.
2. Kuczmarski, R., et al., *CDC growth charts for the US: methods and development.* Vital Health Stat, 2002. **11**(246): p. 1-190.
3. Thum Y. M. and C.H. Hauser, *NWEA 2015 MAP Norms for Student and School Achievement Status and Growth*, in *NWEA Research Report*. 2015, NWEA: Portland, OR.
4. Welk, G. and M.D. Meredith, *Fitnessgram and Activitygram Test Administration Manual-Updated 4th Edition*. 2010: Human Kinetics.
5. Tomkinson, G.R., et al., *Secular trends in the performance of children and adolescents (1980–2000)*. Sports Medicine, 2003. **33**(4): p. 285-300.
6. Beets, M.W. and K.H. Pitetti, *One-mile run/walk and body mass index of an ethnically diverse sample of youth*. Medicine and Science in Sports and Exercise, 2004. **36**(10): p. 1796-1803.
7. Beets, M.W. and K.H. Pitetti, *A Comparison of 20-M Shuttle-Run Performance of us Midwestern Youth to Their National and International Counterparts*. Pediatric Exercise Science, 2004. **16**(2): p. 94-112.
8. Beets, M.W., K.H. Pitetti, and B.J. Cardinal, *Progressive aerobic cardiovascular endurance run and body mass index among an ethnically diverse sample of 10-15-year-olds*. Research Quarterly for Exercise and Sport, 2005. **76**(4): p. 389-397.

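### As listed, the covariates do not adjust the non-randomised 21C change contrasts for zBMI, MAP and PACER; these rest on unstated parallel trends, and baseline's role in the model is contradictory

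*Combined protocol and SAP*

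**What the plan says.** The Trial Design section calls the study quasi-experimental and compares HSL with 21C and with no program, 60 children each. On allocation, the Randomization section states: "Children will not randomly assigned to the 21C program as the participating school declined random assignment of these children". The other 120 children are randomised between HSL and control.

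The Data Analysis section fits one multilevel mixed model per outcome to all three arms. The terms are group, "time (baseline, post-summer, post schoolyear), and all group-x-time interactions". On covariates it adds: "All analyses will include baseline scores on the dependent variable, age, gender, race, and year of participation as covariates in the models". The only interactions named are group by time. Missing data are left to full information maximum likelihood. No contrast is named as the main one, no parallel-trends assumption is stated, and no analysis addresses selection into 21C.

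Some protection comes from the design. Under Participants, every child meets the criteria the district applied for 21C (MAP reading between the 25th and 75th percentile, no severe intellectual disability). Under Interventions, 21C and HSL children come from the same school.

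**The concern.** Two of the three possible contrasts involve an arm that was not randomised, and one of them, HSL versus 21C, is a stated comparison. The covariate list is the only part of the model that could account for differences between children who entered 21C and the rest. Whether it does so depends on how the covariates enter. A covariate that acts equally at every time point explains level, not change, and the program effect in this model is a difference in change.

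Suppose 21C children would have changed differently over the summer for reasons tied to age, gender or race. That difference would then pass in full into the 21C estimates. With no contrast designated, the randomised and non-randomised estimates would also stand side by side with nothing to separate them.

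**Working it through.** **1. Counts.** 2 × 90 = 180; 3 × 60 = 180; 180 − 60 = 120 = 60 + 60. All agree with the plan. No effect size, SD or power is given, so 60 per arm cannot be re-derived. Each summer 90 − 60 = 30 children are in 21C, so year is balanced between 21C and the rest.

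**2. Algebra.** Write `y(i,t) = mu(g,t) + x(i)·b + error`, with `x(i)` constant over time. With complete data and a common covariance matrix, the fitted cell mean is `ybar(g,t) − xbar(g)·b`. The term `xbar(g)·b` is the same at baseline and post-summer, so it drops out of each arm's change and of every difference in change. This also holds for the baseline score entered as a covariate.

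**3. Numerical check** (all parameters assumed). 200 simulated trials of 3 × 60 children at three times. The true 21C effect is 0. 21C children differ by 0.8 SD on a measured covariate that moves change by 0.25 per SD, so the expected bias is 0.8 × 0.25 = 0.20 outcome units. They also start 0.3 lower. Mean 21C-versus-control estimate, compound symmetry:

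| Follow-up missing | No covariates | Age, gender, race, year | Plus baseline score |
|---|---|---|---|
| 0% | 0.1941 | 0.1941 | 0.1941 |
| 15% | 0.1930 | 0.1929 | 0.1922 |
| 30% | 0.1913 | 0.1913 | 0.1906 |

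With complete data the largest difference in any trial was 0.000000, under compound-symmetric and unstructured covariance alike. With 30% missing, single trials moved by at most 0.020, or 0.090 once the baseline score was added. HSL versus control averaged −0.004. In a separate run of 500 trials with age-driven selection, the 21C estimate was 0.212 with and without the main effects, and 0.010 with covariate-by-time terms.

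**4. The other reading.** A follow-up-only regression on baseline score and covariates, fitted to the 200 complete-data trials, gave −0.062. The covariate-driven 0.20 is gone. What remains comes from the assumed stable level difference: within-arm reliability is 0.64/(0.64 + 0.16) = 0.8, and −0.3 × (1 − 0.8) = −0.06.

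**5. Possible size, in SD of change.** With 60 per arm the standard error is sqrt(2/60) = 0.183. A shift d gives Z a mean of d × sqrt(30), and the false-positive rate is P(|Z| > 1.96). The simulated columns (20,000 runs each) let age cause the shift, as correlation of age with change × arm difference in age: 0.2 × 0.5, 0.4 × 0.5 and 0.4 × 0.75.

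| Shift d | Mean of Z | Formula | HSL vs 21C, plan | HSL vs 21C, covariates by time |
|---|---|---|---|---|
| 0.1 | 0.548 | 8.5% | 8.8% | 5.1% |
| 0.2 | 1.095 | 19.5% | 19.5% | 5.1% |
| 0.3 | 1.643 | 37.6% | 37.7% | 5.1% |

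The last column uses age, gender, race and year by time. HSL versus control stayed at 4.9% to 5.1%.

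**6. Baseline-outcome adjustment, in SD of the outcome.** At correlation 0.8 the SD of change is sqrt(2 × 0.2) = 0.63 outcome SD, so these shifts are not on the scale of step 5. False-positive rates for a 21C contrast with a 0.5 SD baseline difference:

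| How the arms differ | Change model (plan) | Baseline-adjusted |
|---|---|---|
| Stable level difference | 5.2% | 14.8% |
| Entry to 21C on the baseline score itself | 13.6% | 5.0% |

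Neither model is safe under both.

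**The case against.** - **The text is ambiguous.** The plan never says main effects only, and it lists baseline score as a covariate. Under a follow-up-only model the covariates do adjust. This stands, and it makes the finding conditional. But baseline is expressly a time level, so the two statements conflict and need reconciling in any case.
- **Scope.** Fitbit, screen-time and diet measures are collected continuously with no defined baseline level. This stands: the cancellation is established only for zBMI, MAP and PACER.
- **A change analysis is legitimate.** It is the correct one in the first row of step 6. This stands, and it rules out presenting baseline adjustment as the correction.
- **No selection is demonstrated.** Eligibility and school are shared, non-randomisation is disclosed, all children are in grades 2 to 4, and zBMI is already age- and sex-specific. The 0.3 SD case through age needs arms 0.75 SD apart on age and a correlation of 0.4 with change. This limits the likely size, but it supplies no rule for analysing the 21C contrasts.

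A reader might infer that the 21C estimates are biased; the documents give no evidence of that. A reader might also infer that the randomised comparison is compromised; this selection leaves it alone, although with missing follow-up it still relies on the missing-data assumption. Nor do the documents support saying that a faulty 21C effect would mislead later trials. The Sample Size section claims only that "samples of 60-100 participants provide reliable estimates of statistical and recruitment parameters upon which subsequent large-scale trials can be based", which does not single out the 21C effect.

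**Conclusion.** The point holds in conditional form. If baseline is a time level and the covariates are main effects, then for zBMI, MAP and PACER the list gives no adjustment of the 21C change contrasts in complete data and almost none on average with missing follow-up. Those contrasts remove stable level differences between arms but otherwise assume parallel summer change, which the plan does not say. The result matters most for HSL versus 21C.

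The algebra needs no assumption about selection. The size does: 8.5%, 19.5% or 37.6% false positives apply only if shifts of 0.1, 0.2 or 0.3 SD of change exist. The change is worth making because it is cheap and the present wording contradicts itself, not because bias has been shown.

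**What to change.** 1. State whether baseline is a time level or a covariate in a follow-up-only model.
2. If it stays a time level, enter age, gender and race by time for the 21C contrasts. Year by time is optional, given its balance across arms.
3. Designate HSL versus control as the main, randomised contrast. Report both 21C contrasts as non-randomised and resting on parallel trends.
4. Pre-state a sensitivity analysis showing the 21C contrasts with and without baseline-outcome adjustment. Describe how children entered 21C, and show by arm the already planned "descriptive statistics of programs, child characteristics, and outcome variables at baseline".

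**Cost.** No new data. With age, gender, two-category race and year all by time, the simulated standard error of a 21C contrast rose from 0.182 to 0.184 (about 1%, arms balanced), 0.188 (3%, arms 0.5 SD apart on age) or 0.199 (9%, 1.0 SD apart) when age is unrelated to change. It fell to 0.172 when age correlated 0.4 with change (arms 0.5 SD apart). Three time levels mean at least two coefficients per covariate, so at least 3 × 2 = 6, and more if race has more than two categories. There is also one extra table and more cautious wording for 21C. The terms handle measured selection only; the report should say that unmeasured selection can remain.

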Fitbit data. Children will be asked to wear the Fitbit device every day for the entire summer (i.e., 12 weeks) starting the last week of school in the spring (May) until the first week of school in fall (August). Parents will be sent text reminders to sync and charge their child's Fitbit device every 3-4 days. Only days with >10 hours of waking wear [14] will be considered valid. Data processing will be informed by the ISCOLE data processing protocols [14].

Consistent with previous studies [15-18], daily resting heartrate for each child will be distilled into activity intensity levels by identifying the average of the lowest 10-mins beats-per-minute during wake time for each day. Resting heartrates above the 95th (90bpm), or below the 5th (50bpm) percentile will be considered implausible and replaced with the closest day that the child had a plausible resting heartrate. Percent heart rate reserve (HRR) will be calculated using the following formula
$$\frac{\text{heart rate}-\text{resting heart rate}}{\text{maximum heart rate}-\text{resting heart rate}}$$
 and will be used to determine activity intensity levels, with 0.0-19.9% of HRR as sedentary, and $\geq 50.0\%$ as MVPA.²⁸⁻²⁹ Maximum heart rate was defined as 197 beats per minute for all children [19]. Sleep will be identified and parsed from activity.

Sleep onset will be defined as the first minute that the sleep episode began. Sleep offset will be selected as the last minute that a sleep episode was recorded. The sum of the minutes that the Fitbit device classifies a child as asleep during a sleep episode will be considered total sleep time. Only nocturnal sleep will be considered for this study and will be defined as sleep onset that occurred between 5pm and 6am and lasted for greater than 240 minutes [20]. Sleep segments separated by less than 20 minutes will be considered one continuous sleep segment.

Screen Time and Diet

Parents will complete the following measures through an online survey that will be texted to their smartphone twice per week (i.e., one weekday and one weekend day) during the 12-week period that children wear the Fitbit device and will be encouraged to discuss their estimates with children to improve accuracy.

Parents will be asked to estimate the total amount of time (hours and minutes) their child spends in front of a screen taht day (e.g., TV, computer, video game, smartphone, and tablet).

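### Fitbit and screen-time outcomes yield many records per child per period with no averaging rule; entered as rows with only a child intercept, they make group-by-time standard errors too small

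*Combined protocol and SAP*

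**What the plan says.** The Data Analysis section specifies a single model form for all dependent variables: "Multilevel mixed effects linear regressions with measures nested within children will be estimated". Its fixed effects include group, "time (baseline, post-summer, post schoolyear), and all group-x-time interactions". The section does not list the random effects, a residual correlation structure or robust standard errors.

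The behavioural outcomes are recorded far more often than the time factor has levels. Under Physical Activity & Sleep: "Children will be asked to wear the Fitbit device every day for the entire summer (i.e., 12 weeks". The validity rule is by day, "Only days with >10 hours of waking wear [14] will be considered valid", with no minimum number of days and no rule for averaging over days. Under Screen Time and Diet, parents are surveyed "twice per week (i.e., one weekday and one weekend day" over the same 12 weeks. Diet alone has a stated summary, a mean number of days per week, but the span it covers is not given. BMI, MAP reading and PACER are single assessments per occasion.

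On error control, the per-test level is 0.05, and "The Benjamini-Hochberg procedure with a false discovery rate of 10% will be utilized to account for multiple comparisons".

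**The concern.** In a model with only a child intercept, the group-by-time effect is judged against the residual. If each row is a day, that residual is mostly day-to-day noise. Children also differ in how much their own behaviour shifts from school to summer, and an arm comparison of change has to be judged against that variation too. Without a term for it, each extra day of wear counts as fresh evidence about the difference between arms, when it only measures the same child's shift more precisely. Serial correlation between days acts in the same direction.

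The Trial Design section says that HSL works through children's obesogenic behaviours. The results for activity, sedentary time, sleep and screen time carry that mechanism claim, and they are the ones whose intervals could be too narrow. The Benjamini-Hochberg step does not help, because it takes the p-values as valid and cannot repair a standard error.

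**Working it through.** **Inputs from the documents.** Children per arm: "The above selection criteria will yield 60 children in each arm of the study". Per-test alpha is 0.05 (two-sided assumed). Maximum records per child are 12 × 7 = 84 Fitbit days and 12 × 2 = 24 surveys.

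**Assumed inputs.** The documents give no variance components and do not say which weeks form each time level. I take a day-to-day SD σ = 20 min, 5 valid baseline days, 5, 25 or 50 valid later days, and an SD of child-specific change τ = 5, 10 or 15 min. Two periods are used, because Fitbit wear is described only from May to August. The child intercept and the covariates are constant within a child, so they cancel from the change contrast when all children have the same row counts.

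**Formulas.** With m0 and m1 rows in the two periods and h = 1/m0 + 1/m1:

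- True variance of the arm difference in change: (2/60) × (τ² + σ²h)
- Variance the intercept-only model reports: (2/60) × h × s², where s² = [(τ²/h + σ²) + σ²(m0 + m1 − 2)] / (m0 + m1 − 1)
- Actual type I error: 2 × [1 − Φ(1.96 × √(model variance / true variance))]

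**Recovering the plan's 5%.** With one row per period, h = 2 and s² = τ²/2 + σ², so h × s² = τ² + 2σ². This equals the true term, and type I error is 5.0% for any τ. With τ = 0 and independent days, s² = σ², and the result is again 5.0% for any number of rows.

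**One cell in full (5 + 25 days, τ = 10).**

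- h = 0.20 + 0.04 = 0.24
- True term: 100 + 400 × 0.24 = 196
- s² = [(100/0.24 + 400) + 400 × 28] / 29 = 414.4, so the model term is 0.24 × 414.4 = 99.4
- Standard errors: true √(196/30) = 2.56 min, reported √(99.4/30) = 1.82 min, ratio 0.71
- Type I error: 2 × [1 − Φ(1.96 × 0.71)] = 16.3%

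**All cells (type I error).**

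| Later days | τ = 5 | τ = 10 | τ = 15 |
|---|---|---|---|
| 5 | 6.6% | 11.2% | 17.4% |
| 25 | 7.9% | 16.3% | 26.5% |
| 50 | 8.3% | 17.5% | 28.8% |

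Simulation agreed: 15.5% for 25 later days and 17.3% for 50, both at τ = 10. A test on each child's change in period means stayed at 4–6% throughout.

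**Serial correlation.** A day-to-day correlation of 0.3 with no child-specific change gave about 11–14%. Combined with τ = 5 and 25 later days it gave about 15–16%.

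**Other row structures.** Let r be the child-by-period variance divided by the record-level residual variance, so that τ² = 2rσ². Over r = 0.05 to 0.50, type I error is 7.0–22.6% for twice-weekly surveys (2 + 22 rows), 6.0–14.1% for weekly means (1 + 11 rows) and 12.5–45.5% for complete Fitbit wear (7 + 77 rows).

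**The case against.** A reader might infer that the plan commits to day-level rows with a single random intercept, and so that its false-positive rate does exceed 5%. The documents do not support that. They never say that daily or survey records enter separately, and they list no random effects; a child-specific slope on time would also fit the wording. Three features point partly towards averaging: time has three levels rather than days or weeks, every model carries a baseline score as a covariate (so baseline days must be reduced to one value), and diet is already summarised as a mean. If the time levels are the last school week in spring and the first in autumn, there are only about 5 later days, and the smallest figure above, 6.6%, could apply.

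A reader might also infer that the main results are compromised. They are not: zBMI and MAP reading (primary) and PACER (secondary) have one value per occasion.

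These limits stand, and they make the finding conditional. They do not remove it. The baseline covariate does not stop summer days from entering as rows. For MVPA, sedentary time and sleep, the only units the plan defines are the day and the night, and no averaging sentence matches the one for diet. An analyst could follow the stated nesting on the stated data exactly and obtain intervals that are too narrow.

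**Conclusion.** The concern holds in conditional form. For the Fitbit outcomes and screen time, the plan permits, and read literally describes, an analysis whose group-by-time standard errors are too small. The condition is that records enter as separate rows with only a child intercept, and that children differ in their change or days are serially correlated. Under the assumed variances, type I error is about 7–17% with 5 later days and 8–29% with 25 to 50, against a nominal 5%. The direction does not depend on those assumptions; the size does, and it also depends on which weeks define each time level.

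There is no inflation with one value per child per period, or with neither child-specific change nor serial correlation. Diet is affected only if its mean is computed more than once per period. This should be settled before these outcomes are analysed.

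**What to change.** State in the Data Analysis section the unit of analysis for the Fitbit outcomes and screen time (and for diet, if it has several rows per period), and the dates that define each time level. Then choose one of two analyses:

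1. Analyse one mean per child per period.
2. Keep record-level rows, add a child-by-period random effect, and use child-clustered robust standard errors. The robust errors cover serial correlation within a period, which the random effect alone may not absorb.

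With unequal numbers of valid days the two are close but not identical. Weighting each mean by its number of valid days does not reproduce option 2: such weights are optimal only when children do not differ in their change, which is the case where the problem does not arise.

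The cost is a few sentences of SAP text and one model option. Intervals will be wider where child-specific change or serial correlation is present.

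No change is needed on this ground for zBMI, MAP reading or PACER.

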Interventions to Promote Healthy Lifestyle and Academic Performance in Children During the Summer Months.

NCT03321071

June 4th, 2020

Methods

Trial Design

This study is a three-armed quasi-experimental study employing a repeated measure within and between participant design comparing the HSL (n=60), to 21C (n=60), and no program (n=60). HSL is designed to mitigate academic learning loss and accelerated summer BMI gain by positively impacting children's obesogenic behaviors.

Participants

To distribute the costs of operating HSL the study takes place over two summers (i.e., June-August, 2018 & 2019). A single elementary school in the Columbia, SC metropolitan area will participate each summer (i.e., two schools, one each summer). Schools will be selected because they serve children from low-income households (100% free and reduced priced lunch) and they operate a 21C summer program. Inclusion criteria are that children are in the 2nd, 3rd, or 4th grade and their standardized reading score on the Measures of Academic Progress is between the 25th and the 75th percentile. Exclusion criteria is the presence of a severe intellectual disability (e.g., fragile X syndrome, severe autism). Measures of Academic Progress scores between the 25th and the 75th percentile and the absence of a severe intellectual disability were chosen as inclusion/exclusion criteria because these are the criteria the school district used to select children to participate in the 21C. A total of 90 students will participate each summer (i.e., 180 participants total). Participants will be assigned to one of three conditions HSL (n=60), 21C (n=60), or no program (n=60).

Interventions

HSL was designed in partnership with the local school district in which the study will occur. HSL was designed to, (1) address summer declines in reading achievement and (2) mitigate accelerated unhealthy weight gain during the summer by positively impacting children's obesogenic behaviors. HSL will operate at the participating schools and will be delivered by certified teachers. Participants enrolled in HSL will attend daily (Monday-Thursday, 8:00-15:30) for six weeks during the summer, with a one-week break in the middle of the program (i.e., 4th of July). The program day will consist of alternating sixty-minute periods of physical activity (3

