Follow-up assessments will be conducted 3-months following baseline. For Physical Activity, Sleep, Screen Time, and Diet measures will be collected continuously from baseline to outcome.

Body Mass Index – Primary Outcome. Following standardized protocols trained research assistants will collect children's heights (nearest 0.1 cm) and weights (nearest 0.01 lbs.) without shoes in light clothing using a portable stadiometer (Model S100, Ayrton Corp., Prior Lake, Minn.) and digital scale (Healthometer model 500KL, Health o meter, McCook, Ill.). BMI will be calculated ($BMI = \text{kg}/\text{m}^2$) and transformed into age and sex specific z-scores (zBMI) according to the Centers for Disease Control growth charts [2].

Measures of Academic Progress Reading Scores – Primary Outcome. Children's reading achievement will be assessed via the MAP reading assessment. Created by the Northwest Evaluation Association (www.nwea.org), MAP results are widely accepted and used extensively in school-aged children [3]. Scores are reported using the Rasch Unit Scale, a curriculum scale developed using Item Response Theory that estimates student achievement. The Rasch Unit Scale ranges from 140-300 and are norm referenced based on grade [3]. MAP reading assessment will be administered as part of typical curriculum in the fall (first month of school) and end of the spring (last month of school) of each year.

Cardiorespiratory Fitness – Secondary Outcome. The Progressive Aerobic Cardiovascular Endurance Run (PACER) will be administered during regularly scheduled PE [4-10]. The PACER will be carried out by a trained research assistant and the PE teacher following standardized protocols on a marked outdoor green space.

Physical Activity & Sleep – Physical activity (MVPA, sedentary time) and sleep (total sleep duration, sleep onset, sleep offset, midpoint) will be measured using a Fitbit Charge 2TM (Fitbit Inc., San Francisco, California, USA). Fitbit Charge 2 devices have demonstrated initial reliability and validity for detecting heartrate and sleep [11-13]. Each Fitbit will be assigned a unique numeric identifier and each device will be linked to Fitabase (San Diego, CA, USA) a web-based interface that allows remote access and download of participants' second level

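### Baseline enters the mixed model both as an outcome and as a covariate, so with complete data none of the five covariates adjusts the group-by-time effect, and the 21C estimand is left unstated

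*Combined protocol and SAP*

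**What the plan says.** The Data Analysis section gives one model for every outcome: "Multilevel mixed effects linear regressions with measures nested within children will be estimated". Its fixed effects include dummy-coded group and "time (baseline, post-summer, post schoolyear), and all group-x-time interactions", so the baseline measurement is one of the modelled responses. The next sentence adds: "All analyses will include baseline scores on the dependent variable, age, gender, race, and year of participation as covariates in the models". The plan does not say that baseline rows are dropped, that any covariate interacts with time, or which coefficient or contrast is the treatment effect.

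Three other sections bear on this:

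- **Randomization.** HSL versus no program is randomised. For 21C: "Children will not randomly assigned to the 21C program as the participating school declined random assignment of these children".
- **Outcomes.** For BMI, MAP reading and fitness: "Follow-up assessments will be conducted 3-months following baseline". This describes one follow-up, whereas Data Analysis lists two times after baseline. Behaviours are handled differently: "For Physical Activity, Sleep, Screen Time, and Diet measures will be collected continuously from baseline to outcome".
- **Sample Size.** Samples of the planned order are justified because they "provide reliable estimates of statistical and recruitment parameters upon which subsequent large-scale trials can be based".

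**The concern.** Baseline can be handled in either of two standard ways. It can be a response, with the effect read from group-by-time, or a covariate, with only follow-up values modelled. Doing both in one model does not combine their benefits. The covariate list suggests an effect adjusted for baseline, age, gender, race and year, but the group-by-time coefficient may not be adjusted for any of them.

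This matters most for 21C, where selection into the arm is not random and readers would lean on the adjustment. A difference in change and a difference conditional on baseline rest on different assumptions and can disagree. If the plan does not choose, the choice can be made after the results are seen. For HSL versus control the stake is precision and, in one configuration, the validity of the standard error. The same model serves both primary outcomes.

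**Working it through.** **Inputs.** From the documents: 60 children per arm, three arms, five covariates entered as main effects, and time including baseline. Nested measures are read as a child random intercept, and age as age at enrolment. The documents give no correlation r between baseline and follow-up, no 21C baseline gap and no dropout rate. Assumed: r = 0.5, 0.8, 0.95 (results below in that order), a gap of 0.3 SD, and 20% missing where stated.

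**1. Cancellation.** With a free mean for every group and time, a time-constant covariate x with slope c shifts all time means of group g by the same c·x̄_g. In (follow-up − baseline) for one group minus the same for control, that shift drops out. With complete data this holds whatever the within-child covariance.

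**2. Numerical check.** Simulated data, 3 × 60, two waves, r = 0.5. 21C was generated 0.3 SD higher at each wave and 0.5 SD older; change rises 0.2 SD per SD of age.

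| Analysis | HSL | 21C |
|---|---|---|
| Raw difference in mean change | −0.0678 | −0.1609 |
| Group-by-time, no covariates | −0.0678 | −0.1609 |
| Group-by-time, baseline added | −0.0678 | −0.1609 |
| Group-by-time, all five covariates | −0.0678 | −0.1609 |
| ANCOVA on baseline | +0.0196 | −0.0521 |
| Covariate-by-time terms, no baseline covariate | −0.0525 | −0.2974 |

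A separate three-wave data set (r = 0.6, 21C generated 0.6 SD lower at baseline) gave the same invariance. Its four coefficients (−0.005474, 0.045803, −0.119205, 0.523463) agreed to six decimals with none, one or all five covariates. The invariance also held with compound-symmetry and unstructured covariances held fixed.

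**3. Precision, HSL versus control.** Per child, the variance of change is 2σ²(1 − r) and the ANCOVA residual variance is σ²(1 − r²). The ratio is 2/(1 + r) = 1.33, 1.11, 1.03, so 60 per arm is worth 60(1 + r)/2 = 45, 54, 58.5.

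For MAP, eligibility requires that "their standardized reading score on the Measures of Academic Progress is between the 25th and the 75th percentile". If that score is the baseline and is normal, truncation at ±0.674 SD leaves variance 0.143 (SD 0.378 of the population SD). The ratio is then 1 + 0.143(1 − r)/(1 + r) = 1.05, 1.02, 1.004, so 60 is worth 57.3, 59.1, 59.8.

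**4. 21C estimands.** Change subtracts 1 × gap and ANCOVA subtracts about r × gap, so they differ by (1 − r) × gap. For 0.3 SD this is 0.15, 0.06, 0.015 SD. For MAP, with 0.3 restricted SD, it is (1 − r) × 0.3 × 0.378 = 0.057, 0.023, 0.006 population SD. In 1000 simulated trials (r = 0.6, gap 0.6 SD, no effect conditional on baseline), the mean 21C estimate was +0.246 SD from change and +0.006 SD from ANCOVA. The formula gives 0.4 × 0.6 = 0.24.

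**5. Standard error with one follow-up and a random intercept.** The single baseline slope settles at (1 + r)/2, a compromise between 1 in the baseline row and r in the follow-up row.

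- The two residuals then have covariance −σ²(1 − r)²/4. This is negative, so the intercept variance is estimated as zero.
- The average residual variance is σ²(1 − r)(3 + r)/4, so the model takes the variance of change as σ²(1 − r)(3 + r)/2 against a true 2σ²(1 − r). The ratio is (3 + r)/4.
- Type I error is 2[1 − Φ(1.96·√((3 + r)/4))] = 6.7%, 5.6%, 5.1%.

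Simulated type I error for the other settings (4000 replicates each, Monte Carlo SE about 0.35 points):

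| Setting | With baseline covariate | Without |
|---|---|---|
| One follow-up, 20% missing completely at random | 9.6, 9.0, 8.3% | 5.5, 5.5, 5.1% |
| Three waves, complete, equal correlation | 5.6, 4.9, 5.2% | same |
| Three waves, 20% missing | 6.8, 6.0, 5.7% | 5.5, 4.9, 4.3% |

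**6. Fitted between-child variance, without and with the baseline covariate.** Two waves: 0.499 and 0.000 (r = 0.5), 0.705 and 0.000 (r = 0.8). Three waves: 0.417 and 0.048, 0.646 and 0.050.

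**The case against.** **The plan names no contrast.** The same fit also yields the group difference at post-summer (group main effect plus interaction), and the covariates do move that. In the three-wave data set the 21C difference goes from −0.621 + 0.046 = −0.575 to −0.152 + 0.046 = −0.106, near the ANCOVA value of −0.129. This is true, but it does not rescue the model. The slope applied to the baseline gap lies between r and 1 because the baseline rows pull it upward, so the result is neither a change estimand nor a conditional one.

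**Complete data is not the planned setting.** The plan uses full information maximum likelihood. With 20% of follow-up values missing the covariates do enter the contrast (21C 0.188 to 0.145 in that data set), and they can support a missing-at-random assumption. That stands, but it is a by-product of missingness and not confounder adjustment.

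**The analysis text lists three waves.** With three waves the standard error is nearly unaffected, and the 8% to 10% error rates need both one follow-up and an assumed dropout. This stands. Fall and spring MAP testing also makes a third wave plausible for that outcome.

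**The sizes rest on assumptions.** This stands too. Recruiting by the district's own 21C reading criteria limits the MAP gap, and at r = 0.95 the precision and 21C figures are negligible.

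**An unadjusted between-child variance can still be computed.** It can, but the planned model would not report it.

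**Conclusion.** The concern holds and should be fixed. For outcomes with one value per wave and complete data, the planned group-by-time effect is the raw difference in mean change, and the five listed covariates do not alter it. That much is algebra and depends on no assumed figure.

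The consequences vary in size:

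- **HSL versus control:** unbiased. The cost is precision, from a quarter of the effective sample at r = 0.5 (45 of 60) to almost nothing at r = 0.95, and little for MAP.
- **21C:** the estimand is undefined between two defensible readings that differ by (1 − r) times an unknown baseline gap. Age, gender and race give this contrast no protection.
- **Standard error:** too small if there is one follow-up and a random intercept, and more so with dropout; small or no effect with three waves.
- **Later trials:** the fitted between-child variance is no longer a usable design parameter, which weakens the stated purpose of the sample size.

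**What to change.** Use baseline once and name the contrast, for example group by post-summer.

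- **HSL versus control,** one of two options. (a) Keep baseline as an outcome row, remove it from the covariate list and constrain the two randomised arms to a common baseline mean. (b) Model follow-up rows only, with baseline and baseline-by-time as covariates; with one follow-up this is plain ANCOVA.
- **21C:** state whether the target is the difference in change (option a, with the 21C baseline mean left free) or the difference conditional on baseline (option b).
- **Age, gender, race and year:** under (a), add their interactions with time wherever they are meant to adjust the contrast, above all for 21C. Under (b) they adjust the follow-up comparison directly.
- **Covariance:** use an unstructured residual covariance only for outcomes with one value per wave, not for daily device or twice-weekly survey data.
- **Consistency:** reconcile the number of waves between Outcomes and Data Analysis, and say how a missing baseline is handled.

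In simulation with one follow-up and 20% missing, ANCOVA held type I error at 4.7%, 4.5% and 4.8%. Its mean standard errors were 0.177, 0.123 and 0.064, against 0.199, 0.128 and 0.064 for the random-intercept change model without the baseline covariate.

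The cost is SAP wording and a few lines of Stata, with no new data. The drawbacks are a few more parameters, a common-baseline constraint that rests on randomisation and cannot extend to 21C, and, under (b), a need for imputation or a joint likelihood to keep children without a baseline value.
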